- 1) To compare adherence among persons across the three study arms.
- 2) To evaluate the safety, tolerability and acceptability of treatment in the three arms.

3. Background

Globally, an estimated 70 – 80 million persons are chronically infected with hepatitis C (HCV). Chronic hepatitis C is associated with long-term complications including liver cirrhosis, hepatocellular carcinoma and end-stage liver disease. Chronic hepatitis C is treatable and treatment can cure infection such that HCV RNA is undetectable and persons cannot transmit virus and risk for chronic complications decreases substantially. Treatment access has been hampered in much of the world in part due to the low efficacy and toxicity of the previous generation of regimens. The landscape of HCV treatment has changed dramatically over the past few years with the FDA approval of highly efficacious, non-toxic second generation direct acting antiviral agents. With these advances in treatment, questions have arisen about delivery of these agents among populations in resource-limited settings (RLS) given some of the inherent differences in HCV infected patients in these settings. Ideally, a treatment regimen for RLS should be pan-genotypic; thereby, not requiring HCV genotype testing which can be cost prohibitive and rarely available in these settings. Moreover, treatment delivery strategies need to optimize adherence particularly in populations that have had suboptimal adherence such as people who inject drugs (PWID).

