All subjects will complete screening, baseline, end-of treatment and post-treatment assessments. All of these assessments will take place in the YRG-JHU ICC in Bilaspur. Screening assessments will be completed within 28 days of the Baseline/Day 1 visit. Participants in all three arms will be asked to complete 4 study visits: 1) Screening; 2) the Baseline/Day 1 of treatment visit; 3) End of treatment visit (at 4 weeks for participants in Arm 1 and at 12 weeks for participants in Arms 2 and 3); and 4) 12 weeks post treatment completion visit (SVR12). In addition, subjects in Arm 1 will need to visit the clinic for an additional 3 visits to receive their PEG injections and participants in Arm 3 will need to come in at Weeks 4 and 8 for medication refills. Finally, subjects in Arms 1 and 2 will receive daily visits from field staff to receive their study medications.

The details of procedures at each visit are listed below. Information on laboratory parameters to be measured and details regarding the clinical assessments that will be performed are provided in 4a5.6.

4a3. Screening and Consent Procedures

Subjects will complete all screening assessments within 28 days of the Baseline/Day 1 visit. Written informed consent will be obtained from subjects prior to the assessment of study eligibility. Those who fail to satisfy eligibility criteria for the trial will still be able to receive services provided by the ICC. If they are still visiting the ICC, they will be allowed to re-screen for the pilot trial if they were excluded because of a modifiable exclusion criteria (e.g., Platelet count <50,000 cells/ml).

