Subjects in Arm 1 will be required to visit the Bilaspur ICC once weekly for four weeks. During these visits, participants in Arm 1 will receive their pegylated interferon alfa-2a shots subcutaneously at the clinic by a registered medical practitioner. They will be compensated INR 100 (USD 1.5) for these visits (since this is not the standard of care).

Subjects in Arms 1 and 2 will also receive 3 doses of SOF and DAC, which they will be instructed to take home and use as backup in case there is a problem receiving the daily medication from field workers. Otherwise, all doses of SOF and DAC will be delivered as directly observed therapy (DOT) daily in the field including Saturday and Sunday doses. Peer-health workers (PHW) (1 per 15-20 participants: total 4 for the study) will deliver the SOF and DAC via DOT on a daily basis to a location of the participant's choosing. We will provide the PHW with laptops/tablets that have a fingerprint reader to record the daily delivery of SOF and DAC and also to also ensure that the drugs are being delivered to the correct participant.

Subjects in Arm 3 will receive their first 4 weeks of treatment supply at baseline and two refills of 28 day's worth of doses at Weeks 4 and 8.

Dose Reduction

If a serious adverse reaction develops in Arm 1 participants during the course of treatment (See Section 8c), the dose of PEG will be modified according to standard guidelines until the AE abates or decreases in severity. See Table 1 for procedures related to depression and see Table 2 for procedures related to hematologic abnormalities. Selective serotonin reuptake inhibitors are available through government hospitals in India and will be made available to study subjects as needed. If persistent or recurrent serious adverse events develop despite adequate dosage adjustment, treatment will be discontinued.

Table 1. Procedures for Dose modification for serious adverse events related to depression

Depression Severity	Initial Management (4-8 weeks)		Depression		
	Dose modification	Visit Schedule	Remains stable	Improves	Worsens
Mild	No change	Evaluate once weekly by clinician at visit and daily recording of symptoms by outreach worker in field	Continue weekly visit schedule	Continue weekly visit schedule	(See moderate or severe depression)

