Peglyated-interferon alfa-2a is commercially available as Taspiance by Emcure Pharmaceuticals in India and will be provided in this study as 180 µg/0.5 mL pre-filled syringes. Each syringe is to deliver 0.5 mL of drug product. The formulation, which is subcutaneously administered, contains sodium chloride, polysorbate 80, benzyl alcohol, sodium acetate trihydrate, acetic acid, and water for injection. The solution is colorless to light yellow and the pH is 6.0 ± 0.5.

Packaging and Labeling

The PEG will meet all applicable requirements of Good Manufacturing Practices: Manufacture of

investigational medicinal products (July 2003) and the Drug Controller General India (DCGI).

Storage and Handling

Peglyated-interferon alfa-2a prefilled syringes will be stored in the refrigerator at 2 °C to 8 °C (36 °F to 46 °F) protected from light and will not be frozen or shaken. Syringes are for single use only.

b. Justification and safety information if FDA approved drugs will be administered for non-FDA approved indications or if doses or routes of administration or participant populations are changed.

N/A

c. Justification and safety information if non-FDA approved drugs without an IND will be administered.

N/A

7. Study Statistics

a. Primary outcome variable.

The primary outcome will be sustained virologic response (SVR12), which is defined as HCV RNA < lower limit of quantification 12 weeks after treatment completion.

b. Secondary outcome variables.

Adherence for comparison across the three arms will be defined using a combination of the biometric data for Arms 1 and 2 and self-report and pill counts for Arm 3. Serious adverse events requiring dose modification or treatment discontinuation will include primarily laboratory abnormalities including anemia, neutropenia and thrombocytopenia. For any adverse event outcome, we will consider occurrence of any of the side effects commonly associated with treatment with pegylated interferon alfa-2a, including but not limited to fatigue, headache, pyrexia, myalgia, rigors, insomnia, nausea, alopecia, irritability, arthralgia, anorexia, dermatitis, depression, or fatigue.

c. Statistical plan including sample size justification and interim data analysis.

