All analyses will be conducted as intention to treat. We will use a chi-squared test of proportions to compare the proportions that achieve SVR12. Pairwise comparisons with correction for multiple comparisons will be conducted to directly compare Arms 1 and 2, Arms 1 and 3 and Arms 2 and 3. For secondary outcomes, chi squared tests of proportions will be used to compare categorical outcomes and a Wilcoxon rank-sum test will be used to compare adherence.

The primary objective of this study is to test the feasibility of DOT for HCV treatment among HCV-infected persons with substance use history in a resource limited setting. An additional objective is to generate pilot data to plan a larger powered study. We hypothesize that SVR12 will be higher in Arm 1 compared to Arms 2 and 3. Assuming a two-sided $\alpha=0.05$, 50 people in each arm and 70% achieving SVR12 in Arm 3, we will have >80% power to detect a difference of 25% (e.g., 95% completion in the SOF+DAC+PEG).

No interim analyses will be conducted as with 150 participants, it will not be possible to observe statistical differences prior to the completion of the trial.

d. Early stopping rules.

As we do not plan to do interim analyses, the only reason for stopping the trial would be a higher frequency than expected of serious adverse events. We will continually monitor the frequency of serious adverse events and if this frequency is 10% or higher, we will prematurely stop the trial.

8. Risks

a. Medical risks, listing all procedures, their major and minor risks and expected frequency.

It is anticipated that most participants who complete their full course of treatment with optimal adherence will clear hepatitis C from their bodies. However, for those individuals who do not respond to treatment, it is possible that non-response will affect their ability to respond to other drugs for hepatitis C in the future. However, with the newer direct acting antiviral (DAA) regimens, response rates have been demonstrated to be comparable in treatment naïve and prior non-responders. The primary risk related to taking these medications is with respect to side effects associated with pegylated interferon alfa2a.

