All AEs will be assessed by the principal investigator or qualified designee (Study Doctor) and recorded on the AE form. The AE entry will indicate whether or not the AE was serious, the start date (AE onset), the stop date (date of AE resolution), whether or not the AE was related to study drug or a study procedure, the action taken with the study drug due to the AE and the severity of the AE. The principal investigator will be responsible for final review and confirmation of accuracy of events, relationship and severity confirmed by signature on the AE form.

The relationship to the study drug will be assessed using a combination of clinical judgement and the following considerations:

- NO: Evidence exists that the adverse event has an etiology other than the study drug. For serious adverse events, an alternative causality will be provided (e.g., pre-existing condition, underlying disease, intercurrent illness or concomitant medication).
- YES: There is a reasonable possibility that the event must have been caused by the investigational medicinal product.

It should be emphasized that ineffective treatment should not be considered as causally related in the context of AE reporting.

The relationship to study procedures (e.g., invasive procedures such as venipuncture or biopsy) should be assessed using the following considerations:

- NO: Evidence exists that the AE has an etiology other than the study procedure.
- YES: The AE occurred as a result of protocol-mandated procedures such as venipuncture.

The severity grading of AEs will be assessed as Grade 1, 2, 3 or 4 using a standard grading scale for severity of adverse events and laboratory abnormalities. This has been adapted from those used for Industry sponsored trials in the US. For AEs associated with laboratory abnormalities, the event should be graded on the basis of the clinical severity in the context of the underlying conditions; this may or may not be in agreement with the grading of the laboratory abnormality.

8c2. Serious Adverse Events

A **serious adverse event (SAE)** is defined as follows:

Any adverse drug experience occurring at any dose that results in any of the following outcomes:

- Death
- Life-threatening situation (subject is at **immediate** risk of death)
- In-patient hospitalization or prolongation of existing hospitalization (excluding those for study therapy or placement of an indwelling catheter, unless associated with other SAEs)

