- Persistent or significant disability/incapacity
- Congenital anomaly/birth defect in the offspring of a subject who received investigational medicinal product
- Other medically significant events that may not be immediately life-threatening or result in death or hospitalization, but based upon appropriate medical and scientific judgement, may jeopardize the subject or may require medical or surgical intervention to prevent one of the outcomes listed above

Examples of such events are as follows:

- Intensive treatment in an emergency room or at home for an allergic bronchospasm
- Blood dyscrasias or convulsions that do not result in hospitalization
- Development of drug dependency or drug abuse

8c2.1. Classification of Serious Adverse Events (SAEs)

- Death is an outcome of an AE, and not an adverse event in itself. In reports of death due to “Disease Progression,” where no other information is provided, the death will be assumed to have resulted from progression of the disease being treated with the study drug.
- The subject may not have been on the study drug at the occurrence of the event. Dosing may have been given as treatment cycles or interrupted temporarily before the onset of the SAE, but may have contributed to the event.
- “Life-threatening” means that the subject was at immediate risk of death from the event as it occurred. This does not include an event that might have led to death if it had occurred with greater severity.
- Complications that occur during hospitalizations are AEs. If a complication prolongs the hospitalization, it is an SAE.
- “In-patient hospitalization” means the subject has been formally admitted to a hospital for medical reasons, for any length of time. This may or may not be overnight. It does not include presentation and care within an emergency department.
- The investigator should attempt to establish a diagnosis of the event on the basis of signs, symptoms and/or other clinical information. In such cases, the diagnosis should be documented as the AE and/or SAE and not the individual signs/symptoms.

A distinction should be drawn between the seriousness and the severity of the AEs. An AE that is assessed as Grade 4 (potentially life-threatening) should not be confused with an SAE. Severity is a category utilized for rating the intensity of an event; and both AEs and SAEs can be assessed as Grade 4. An event is defined as “serious” when it meets one of the predefined outcomes described above.

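### No safety outcome uses the Grade 1-4 recorded for every adverse event, so the planned comparison counts mild and severe interferon symptoms alike; a small addition would fix this.

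*Combined protocol and SAP*

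**What the plan says.** Secondary objective 2 (Section 2) is this: "To evaluate the safety, tolerability and acceptability of treatment in the three arms". Section 7b turns it into two outcomes.

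- Serious events with a dose action: "Serious adverse events requiring dose modification or treatment discontinuation will include primarily laboratory abnormalities including anemia, neutropenia and thrombocytopenia".
- Any adverse event: "For any adverse event outcome, we will consider occurrence of any of the side effects commonly associated with treatment with pegylated interferon alfa-2a". The list of symptoms that follows is explicitly not exhaustive.

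For the analysis, Section 7c says that "chi squared tests of proportions will be used to compare categorical outcomes". It mentions neither grade nor worst grade per participant. The stopping rule in 7d counts serious adverse events, again without grade.

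Section 8c1.1 requires each event's seriousness, severity and action taken to be entered on the adverse event form. On severity it says: "The severity grading of AEs will be assessed as Grade 1, 2, 3 or 4 using a standard grading scale". Section 8c2.1 keeps severity apart from seriousness: "An AE that is assessed as Grade 4 (potentially life-threatening) should not be confused with an SAE".

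**The concern.** An any-grade excess of side effects in Arm 1 would surprise nobody. Section 8a expects most side effects to come from interferon and calls those of sofosbuvir and daclatasvir rare. The open question is how severe the excess is. Section 6a argues that four weeks of interferon should cause few side effects, and the trial is meant to inform a larger one (7c). Someone weighing 4 weeks with interferon against 12 weeks without it needs the severity as well as the count. Neither named outcome supplies it for symptoms that are not serious and change no dose.

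**Working it through.** **1. Is grade used anywhere in the comparison?**

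| Place | What decides that an event counts | Uses Grade 1-4? |
|---|---|---|
| 7b, first outcome | serious, and dose changed or treatment stopped | no |
| 7b, second outcome | a side effect of the interferon type occurred | no |
| 7c, analysis | chi-squared on categorical outcomes | no |
| 7d, stopping rule | serious, 10% or more | no |
| 8c1.1, adverse event form | every event graded | recorded only |

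The word serious in 7b could follow the definition in 8c2 or the looser use in the titles of Tables 1 and 2. On either reading the first outcome rests on seriousness plus action, not on grade.

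**2. What can the first outcome pick up?** The written dose-modification rules in 4a5.2 concern interferon: "If a serious adverse reaction develops in Arm 1 participants during the course of treatment". They therefore apply to Arm 1 only. Discontinuation for toxicity is open to all arms (4a5.4). Under 4a2, "subjects in Arm 1 will need to visit the clinic for an additional 3 visits to receive their PEG injections", so with the Day 1 dose there are four weekly injections, on about Days 1, 8, 15 and 22. A symptom that starts after the fourth leaves no interferon dose to change.

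**3. Consequence.** Take two Arm 1 participants, one with Grade 1 myalgia and one with Grade 3 myalgia, neither serious and neither with a dose action. Both score 0 on the first outcome and 1 on the second. The planned output cannot tell them apart.

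**4. What would a graded outcome deliver?** The plan has no figure for safety. Its only power statement (7c) concerns SVR12: 95% v 70%, 50 per arm, two-sided 0.05. With a pooled proportion of 0.825, the standard error is √(2 × 0.825 × 0.175/50) = 0.0760 under the null and √((0.70 × 0.30 + 0.95 × 0.05)/50) = 0.0718 under the alternative. Then (0.25 − 1.96 × 0.0760)/0.0718 = 1.41, a power of 92%. This agrees with the stated >80%, and the present point does not depend on it.

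For a risk difference with 50 per arm, use Newcombe's interval built from Wilson limits. With no events in an arm, the upper Wilson limit is z²/(n + z²) = 3.84/53.84 = 7.1%. With no events in either arm the interval is therefore 0 ± 7.1 points. For assumed counts of 5 v 1 it is 8.0 points (−2.2 to 19.5). Power for 10% v 2% (assumed rates) at two-sided 0.05 is about 38%. A graded outcome is thus for estimation, not for a formal test.

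**5. Which time window?** Arm 1 is treated for 4 weeks and Arms 2 and 3 for 12. Follow-up ends at week 16 (4b) or week 17 (Table 3) for Arm 1, and at week 24 for the others. With the same constant event rate in each arm, and a proportion q affected by week 24, Arm 1 would show 1 − (1 − q)^(16/24), or the same with 17/24. For an assumed q of 10% this is 6.8% or 7.2%, a spurious gap of 3.2 or 2.8 points in Arm 1's favour. For q of 5% the gap is 1.6 or 1.4, and for 20% it is 6.2 or 5.4. This affects any adverse event count, graded or not. It is a reason to add a common window and says nothing about how serious the missing grade is.

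A strict 4-week window would end 7 days (168 hours) after the fourth injection. With the 80-hour half-life in 6a3, 0.5^(168/80) = 23% of that dose would remain. At 5 weeks (14 days, 336 hours) it would be 0.5^(336/80) = 5%. A window of about 5 weeks is therefore better.

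**The case against.** The best reply is that nothing is lost. Grade, seriousness and action are on the form for every event, so a table by grade can be produced at the reporting stage, and no planned test, sample size or primary conclusion would change. This stands, and it is why the point is minor. What remains is that choosing the threshold and the window after the results are known, in an open-label trial, is weaker than stating them now.

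The plan also holds partial severity information:

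- Table 1 grades depression as mild, moderate or severe. It halves the interferon dose for moderate and stops it for severe. If serious in 7b follows the table titles, these cases reach the first outcome while interferon doses remain.
- All serious events are reported, and 8c2 gives drug dependency or abuse as an example, so relapse of drug use may be captured there.
- Quality-of-life surveys are taken at baseline, end of treatment and SVR12 in all arms (4a5.1, 4a5.3, 4a5.5). They bear on tolerability, although 7b does not name them as outcomes.

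A reader might infer that a severe excess in Arm 1 would go wholly unseen, or that the dose-action outcome would show no difference. The documents do not support this. Section 4a5.4 allows discontinuation for toxicity on clinical judgement in any arm, and nothing suggests that many Grade 3-4 events would pass without action. The sponsor's earlier pilot, with 12 weeks of interferon, saw no serious adverse events in that arm and no discontinuation for side effects (Sections 3 and 6a). That does not exclude Grade 3 symptoms, but it gives no ground for assuming a high rate.

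**Conclusion.** The point holds as a minor, inexpensive improvement. No outcome, analysis or stopping rule uses the recorded Grade 1-4, so for non-serious symptoms without a dose action the plan compares how many participants are affected but not how badly. This rests on the text of 7b, 7c, 7d and 8c1.1 and on no assumed rate. How much it would matter in practice cannot be sized, because the documents give no adverse event rates by grade; the counts and rates above only illustrate precision and the choice of window. Primary-endpoint validity is not in question. A reader might take the words about dose modification in 7b to mean that the first outcome already reflects grade; 8c2.1 separates the two ideas, so it does not. The laboratory schedule in Table 3 and the unnamed grading scale are separate points and are not relied on here.

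**What to change.** In 7b and 7c:

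1. Add the proportion of participants with at least one Grade 3-4 adverse event starting on or after Day 1, by arm. The start date matters because 8c1 records events from screening.
2. Add a table of each participant's maximum grade by arm.
3. Give pairwise risk differences in the Grade 3-4 proportion with 95% confidence intervals, labelled as estimation.
4. Show these, and the existing any-event outcome, for a common window of about 5 weeks from Day 1 and for the whole study. State beside the whole-study results that treatment is 4 v 12 weeks and follow-up 16 or 17 v 24 weeks.

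The cost is a few lines of text and one table, from data already on the adverse event form. The downsides should be stated with the results: wide intervals, grading by staff who know the arm, and unequal contact. Arm 1 has weekly clinic visits plus daily field visits, Arm 2 has daily field visits, and Arm 3 has no scheduled visit between baseline and Week 4. The common window equalises time since Day 1 but not contact.

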An AE is any untoward medical occurrence in a clinical investigation subject administered medicinal product and which does not necessarily have a causal relationship with this treatment. An AE can therefore be any unfavorable and unintended sign, symptom or disease temporally associated with the use of a medicinal product, whether or not considered related to the medicinal product.

AEs also include the following:

- Pre- or post-treatment complications that occur as a result of protocol mandated procedure (e.g., venipuncture) during or after screening (before the administration of study investigational medicinal product)
- Any pre-existing condition that increases in severity, or changes in nature during or as a consequence of the study investigational medicinal product phase of a human clinical trial will also be considered an AE.
- Complications and termination of pregnancy
- All AEs that occur from the study screening visit onwards and throughout the duration of the study, including the follow-up off study medication period will be recorded as an AE.

An AE does not include the following

- Medical or surgical procedures (e.g., surgery, endoscopy, tooth extraction, transfusion) performed; the condition that leads to the procedure is an adverse event.
- Pre-existing disease or conditions or laboratory abnormalities present or detected before the screening visit that do not worsen.
- Situations where an untoward medical occurrence has not occurred (e.g., hospitalization for elective surgery, social and/or convenience admissions)
- Overdose without clinical sequelae

- Any medical condition or clinically significant laboratory abnormality with an onset date before the consent form is signed and not related to a protocol-associated procedure is not an AE. It is considered to be pre-existing and should be documented on the medical history form.
- Uncomplicated pregnancy
- An induced elective abortion to terminate a pregnancy without a medical reason

8c1.1. Assessment of Adverse Events

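### The any-AE outcome counts only interferon-type side effects, so other recorded AEs drop out of a safety comparison meant to cover all three arms

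*Combined protocol and SAP*

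**What the plan says.** Secondary objective 2 (Section 2) is "To evaluate the safety, tolerability and acceptability of treatment in the three arms". Section 7b turns this into two safety outcomes.

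- **Serious events that change treatment:** "Serious adverse events requiring dose modification or treatment discontinuation will include primarily laboratory abnormalities including anemia, neutropenia and thrombocytopenia".
- **Any adverse event:** "we will consider occurrence of any of the side effects commonly associated with treatment with pegylated interferon alfa-2a", followed by "including but not limited to fatigue, headache, pyrexia, myalgia, rigors, insomnia, nausea, alopecia, irritability, arthralgia, anorexia, dermatitis, depression, or fatigue".

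Section 7c compares categorical secondary outcomes with chi-squared tests of proportions.

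Section 8c1 uses a much wider definition for recording: "An AE can therefore be any unfavorable and unintended sign, symptom or disease temporally associated with the use of a medicinal product", whether or not the product is thought to be the cause. The recording period is equally wide: "All AEs that occur from the study screening visit onwards and throughout the duration of the study", including follow-up off drug. Section 8c1.1 adds: "All AEs will be assessed by the principal investigator or qualified designee (Study Doctor) and recorded on the AE form".

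Pegylated interferon is given in Arm 1 only (Section 4a). The trial is not blinded (Section 4c).

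**The concern.** The outcome used to compare three arms is defined by the expected toxicity of a drug that two of them do not receive. The phrase that leaves the symptom list open adds further examples of interferon side effects. It does not admit events outside that class, and no general AE category or category for the oral drugs is added.

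Two consequences follow. First, AEs that the trial collects do not count in its stated comparison unless they fit the interferon profile, so each arm's any-AE proportion may be too low. Second, because the list is open, each recorded event must be judged in or out. The plan names no person or procedure for this, and in an unblinded trial the judgement can be made knowing the arm.

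The trial is also meant to supply pilot data for a larger study (Section 7c), so an incomplete safety comparison could carry forward.

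**Working it through.** The plan states no AE rate and no figure for this outcome, so there is nothing to reproduce. The check is a reading of the sections together, then an illustration with assumed rates.

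**Does another planned outcome fill the gap?** The other 7b outcome is limited to serious events that lead to dose modification or discontinuation. Consider a hospital admission in Arm 2 or 3 that is not interferon-type and does not alter treatment. It is an SAE under Section 8c2 but counts in neither 7b outcome. It would enter the SAE stopping rule of Section 7d, which is not a between-arm comparison. Sections 7b and 7c do not say that the full 8c1 data will be compared by arm.

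**What the restriction does to the rates.** Let a be the probability of at least one interferon-type AE and b the probability of at least one other AE, assumed independent.

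- All-AE proportion = 1 − (1 − a)(1 − b)
- Proportion counted under 7b = a
- Proportion missed = b(1 − a), which is never negative

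**Illustration.** Assume a = 50% in Arm 1 and 25% in Arms 2 and 3. The 7b difference is then 25 points in every row. All rates are assumptions.

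| b, Arm 1 | b, Arms 2/3 | Missed, Arm 1 | Missed, Arms 2/3 | All-AE, Arm 1 | All-AE, Arms 2/3 | All-AE difference (points) |
|---|---|---|---|---|---|---|
| 0% | 0% | 0 | 0 | 50% | 25% | 25 |
| 5% | 5% | 2.5 | 3.75 | 52.5% | 28.75% | 23.75 |
| 15% | 15% | 7.5 | 11.25 | 57.5% | 36.25% | 21.25 |
| 15% | 21.6% | 7.5 | 16.2 | 57.5% | 41.2% | 16.3 |
| 30% | 20% | 15 | 15 | 65% | 40% | 25 |
| 30% | 15% | 15 | 11.25 | 65% | 36.25% | 28.75 |

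Example, third row: Arm 1 is 1 − 0.50 × 0.85 = 0.575, and Arms 2/3 are 1 − 0.75 × 0.85 = 0.3625. The fourth row treats 15% as the result of a constant background rate over 16 weeks and carries it to 24 weeks: 1 − 0.85^1.5 = 0.216.

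**When the sign changes.** The 7b outcome understates the difference between Arm 1 and the others when b₁(1 − a₁) > b₂(1 − a₂), that is when b₁/b₂ > (1 − a₂)/(1 − a₁). Here the threshold is 0.75/0.50 = 1.5.

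**Other assumed values.** With a = 60% and 30%, the threshold is 0.70/0.40 = 1.75. Then b = 10% in every arm gives 64% v 37%, a difference of 27 points against 30 under 7b. With b = 10% in Arm 1 and 30% in Arms 2/3 it is 64% v 51%, 13 points against 30.

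**Can the documents settle b by arm?** No. Follow-up is 16 weeks in Arm 1 and 24 weeks in Arms 2 and 3 (Section 4b), which favours more background events in Arms 2 and 3. Contact runs the other way: weekly clinic visits and daily field visits in Arm 1, daily field visits in Arm 2, and refill visits at Weeks 4 and 8 in Arm 3 (Sections 4a2 and 8b).

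**The case against.** The case for leaving the outcome alone has four parts.

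- **The list is broad.** It contains non-specific symptoms such as fatigue, headache, nausea and insomnia, which count in any arm without interferon having to be the cause. Section 8a also links infections, suicidal thoughts and relapse of drug use to interferon. The class left out may be small. This stands as a limit on size.
- **The focus has a reason.** Section 8a expects most side effects to come from interferon and calls those of the two oral drugs rare. That concerns drug-related events. An AE under 8c1 need not be drug-related, so it does not show that b is near zero.
- **Nothing is lost.** Every AE is recorded with severity, relatedness and action taken, and nothing forbids an all-AE table. This is true, and it is why the remedy is cheap. But the stated comparison still leaves those events out.
- **The effect may be small against sampling error.** In the 15%/15% row the difference moves by 3.75 points. The standard error of a 50% v 25% difference with 50 per arm is √(0.50 × 0.50/50 + 0.25 × 0.75/50) = 9.4 points, so the shift is about 0.4 standard errors, on a secondary outcome of a pilot. This is fair for that scenario.

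In the other direction, a reader might infer that the undercount is worst in Arms 2 and 3 and that the excess in Arm 1 is therefore overstated, by about 4 points in the 15%/15% row. The documents do not support this. It needs other-AE rates that are roughly equal across arms, or higher in Arms 2 and 3. No rates are given, and follow-up and contact differ by arm in opposing ways.

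**Conclusion.** The point holds as a mismatch between an outcome and its objective. Section 7b gives a definite rule that is narrower than the protocol's own AE definition and is built around one arm's drug. Recorded AEs outside that class are left out of the planned three-arm comparison, and class membership must be judged without blinding.

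Each arm's any-AE proportion can be understated and cannot be overstated. The size is unknown. Under the assumed rates in the table, the loss runs from 0 to about 16 points per arm. The true difference runs from 16.3 to 28.75 points where 7b would give 25, and the 60%/30% example gives a still larger gap (13 against 30). These ranges rest on independence and on invented rates. They show only that the effect may be nil, or may go either way.

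The primary outcome is not affected. The wording should be changed before the data are analysed.

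**What to change.** 1. In Section 7b, define the any-AE outcome as any AE recorded under 8c1 with onset after the first dose, tabulated by arm and severity grade.
2. Keep interferon-type events as a named subset, with its terms listed in advance so that no case-by-case judgement is needed once the arm is known.
3. In Section 7c, compare arms over a common window from first dose (for example the first 16 weeks) or as exposure-adjusted rates, and show full follow-up alongside. Without this, the wider definition would bring in background events over unequal follow-up.
4. State as a limitation that AEs are ascertained less often in Arm 3, which has no daily field visits. The new definition does not remove that difference.

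**Cost.** A change of wording and a little more analysis; the AE form already holds the data. The downside is that background events unrelated to treatment will be counted, which is a reason to keep the interferon-type subset.
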